Treatment therapy will be recorded in the year prior to the IPD.

Baseline blood eosinophil counts will be recorded^v (where valid is defined as a numeric value expressed /L).

Co-morbidities will be examined regardless of when diagnosis relative to the index date was made and include:

- Ischaemic heart disease
- Heart failure diagnosis
- Diabetes diagnosis
- Asthma diagnosis
- Bronchiectasis diagnosis
- Rhinitis
- Eczema
- Osteoporosis diagnosis
- Gastroesophageal reflux disease (GERD)
- Anxiety/depression diagnosis
- Chronic kidney disease
- Hypertension

Note that all of the above co-morbidities (except diabetes) are identified by GP diagnostic read code, ever recorded. Diabetes is identified by GP anti-diabetic drug prescriptions; AND/OR by GP diagnostic read code, ever recorded.

For the baseline and outcome periods, the following will be calculated:

- COPD exacerbations^{vi} and the date of event (each component of the definition will also be analysed separately)

^v closest value to IPD (missing if >5 years either side of IPD).

^{vi} Where an exacerbation is defined as an occurrence* of:

- COPD-related: Unscheduled hospital admission / A&E attendance^{**}; OR
- An acute course of oral steroids prescribed with evidence of a respiratory review^{***}; OR
- Antibiotics prescribed with evidence of a respiratory review^{***}.

*Where ≥ 1 oral steroid course / hospitalisation / antibiotics prescription occur within 2 weeks of each other, these events will be considered to be the result of the same exacerbation (and will only be counted once).

****COPD-related Hospitalisations:** consist of either a definite COPD Emergency Attendance or a definite COPD Hospital Admission; OR a generic hospitalisation read code which has been recorded on the same day as a **Lower Respiratory Consultation**[§] (see below - excluding where the only lower respiratory code recorded on that day was for a lung function test).

*****Evidence of a Respiratory Review** - consists of the following:

- a) Any **Lower Respiratory Consultation**[§] (see below) and
- b) Any additional respiratory examinations, referrals, chest x-rays, or events.

§ Lower Respiratory Consultations - consist of the following:

- a) Lower Respiratory read codes (including Asthma, COPD and LRTI read codes);

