- Development of pneumonia (recorded as absence/presence of, and confirmed via: chest X-ray within a month of a pneumonia diagnosis OR hospitalisation within a month of a pneumonia diagnosis). Note that baseline values will be zero due to study exclusion criteria.
- Development/progression of diabetes
 - Development of diabetes (recorded as absence or presence of) during outcome period for patients (for patients without diabetes at or prior to IPD)
 - Progression of ongoing type-II diabetes treatment to insulin (defined as no insulin prescription during 1 year baseline period AND any insulin prescriptions during 1 year outcome period)
 - Diabetic control (defined as change in HbA1c value prior to starting Seretide® and after IPD)
 - Diabetic medication (defined as change in anti-type-II diabetic medication dosage OR medication type)
- Number of potential severe COPD-related adverse events and date of event including
 - Oral thrush
 - Lower respiratory tract infections
 - Bronchitis
 - Dysphonia / hoarseness
 - Nasopharyngitis (common cold)
 - Sinusitis
 - Hypokalemia (low blood potassium)
 - Muscle or joint pain
- ICS dose (in outcome period only) and date of ICS prescription

Matching will be used if required.

STUDY OUTCOMES

The primary aim of the current study is to identify baseline and outcome characteristics of patients with COPD initiating with Seretide® combination therapy via pMDI and Diskus and to identify and compare the potential benefits of using each device in the delivery of Seretide®. Among other events, the effect of device on the following outcomes will be investigated:

(1) COPD related severe exacerbations

Where an exacerbation is defined as an occurrence^{vii} of:

- COPD-related: Unscheduled hospital admission / A&E attendance^{viii}; OR
- An acute course of oral steroids prescribed with evidence of a respiratory review^{ix};
OR

-
- b) Asthma/COPD review codes excl. any monitoring letter codes;
 - c) Lung function and/or asthma monitoring.

^{vii}Where ≥ 1 oral steroid course / hospitalisation / antibiotics prescription occur within 2 weeks of each other, these events will be considered to be the result of the same exacerbation (and will only be counted once).

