^{viii}**COPD-related Hospitalisations:** consist of either a definite COPD Emergency Attendance or a definite COPD Hospital Admission; OR a generic hospitalisation read code which has been recorded on the same day as a **Lower Respiratory Consultation*** (see below - excluding where the only lower respiratory code recorded on that day was for a lung function test).

^{ix}**Evidence of a Respiratory Review** - consists of the following:

- Antibiotics prescribed with evidence of a respiratory review^{ix}.

(2) COPD related adverse events

Where adverse events include the number of incidences of:

- Oral thrush
- Lower respiratory tract infections
- Bronchitis
- Dysphonia / hoarseness
- Nasopharyngitis (common cold)
- Sinusitis
- Hypokalemia (low blood potassium)
- Muscle or joint pain

(3) Therapeutic index

Therapeutic index = highest dose not causing harm (side effect) / lowest dose that causes benefit (reduced number of severe COPD-related events).

For the highest dose not causing harm: the median dose at which no (any) adverse events occur

For the lowest dose that causes benefit (reduced number of severe COPD-related events): median dose at which patients show no increase in number of exacerbations in outcome

STATISTICAL ANALYSIS

Statistically significant results will be defined as $p < 0.05$ and trends as $0.05 \leq p < 0.10$

Summary statistics will be produced for all baseline and outcome variables, as a complete dataset and by device. For variables measured on the interval or ratio scale, these will include:

Sample size (n) & percentage non-missing

Mean & Variance / Standard Deviation

Range (Minimum / Maximum)

Median & Inter-quartile Range (25th and 75th percentiles)

For categorical variables, the summary statistics will include:

Sample size (n)

Range (if applicable)

Count and Percentage by category (distribution)

Treatment arms will be compared using t-test / Mann Whitney U-test (depending on distribution) for variables measured on the interval/ratio scale and using a chi square test for categorical variables.

a) Any **Lower Respiratory Consultation*** (see below) and

b) Any additional respiratory examinations, referrals, chest x-rays, or events.

* **Lower Respiratory Consultations** - consist of the following:

a) Lower Respiratory read codes (including Asthma, COPD and LRTI read codes);

b) Asthma/COPD review codes excl. any monitoring letter codes;

c) Lung function and/or asthma monitoring.

TIMELINE, DELIVERY AND COSTINGS

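### Adverse events are counted in the baseline year, but neither the stated device comparison nor the harm term of the therapeutic index uses that count

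*Protocol*

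**What the plan says.** Under Study Outcomes, item (2), the Protocol introduces eight conditions with "Where adverse events include the number of incidences of". The list runs from oral thrush and dysphonia, which an inhaler can plausibly cause, to "Muscle or joint pain", which is often long-standing in patients aged 35 or over. No sentence there refers to the patient's earlier record.

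Under Dataset Variables the same eight items appear as "Number of potential severe COPD-related adverse events and date of event including", within a list headed "For the baseline and outcome periods, the following will be calculated". So a dated count will exist for each patient in both years.

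Statistical Analysis promises summaries of every baseline and outcome variable by device. It then names the tests between groups: t-test or Mann-Whitney for interval or ratio variables, chi-square for categorical ones. No covariate is mentioned. Dataset Variables holds matching in reserve and names no matching variables.

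Study Outcomes, item (3), defines the harm side of the therapeutic index thus: "For the highest dose not causing harm: the median dose at which no (any) adverse events occur". The benefit side takes the median dose among patients whose exacerbation count does not rise in the outcome year, which only has meaning against the baseline year.

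**The concern.** The device was chosen in routine practice, so the two groups may differ in what they had before the index date. The Protocol collects the natural correction for this, the baseline-year count of each event, but gives it no role beyond description.

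Two results are exposed. In item (2), a recurrent or long-standing condition recorded again after the index date carries the same weight as one that began on treatment. If such records are equally common in both groups they blur the contrast; if not, they can pass for a device effect. In item (3), a patient whose joint pain is no worse than the year before falls outside the unharmed group if it is recorded again, while a patient whose exacerbations are no worse than the year before counts as having benefited. One ratio then uses two different standards, and its harm side partly reflects prior illness.

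Other outcomes do take history into account. New diabetes is sought only "for patients without diabetes at or prior to IPD", and for pneumonia the Protocol observes: "Note that baseline values will be zero due to study exclusion criteria".

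**Working it through.** The Protocol states no adverse event rate, effect size, sample size or power, so there is no figure of its own to reproduce. The point is settled by the definitions; the arithmetic only shows the possible size.

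**Use of the baseline year, outcome by outcome (Protocol)**

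| Outcome | Treatment of history |
|---|---|
| New diabetes | Limited to patients free of it up to the index date |
| Pneumonia | Baseline cases excluded |
| Benefit term of the index | Judged as no rise in exacerbations |
| Eight adverse events, device comparison | Baseline count derived and summarised, not used in the test |
| Harm term of the index | No reference to baseline |

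**Illustration: inputs, all assumed.** New-onset risk of an event is p = 10% on one device and 15% on the other. A share c of patients has a pre-existing condition that is certain to be recorded again in the outcome year. Two-sided alpha is 0.05 (the Protocol gives 0.05 without stating sides).

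Formula: observed risk = c + (1 − c) × p.

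For c = 0, the standard two-proportion formula with pooled variance under the null gives 686 per group for 80% power. Holding 686 per group:

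| c, both groups | Observed risks | Difference | Ratio | Power |
|---|---|---|---|---|
| 0% | 10.0% v 15.0% | 5.0 points | 1.50 | 80% |
| 10% | 19.0% v 23.5% | 4.5 points | 1.24 | 53% |
| 20% | 28.0% v 32.0% | 4.0 points | 1.14 | 37% |
| 30% | 37.0% v 40.5% | 3.5 points | 1.09 | 26% |
| 50% | 55.0% v 57.5% | 2.5 points | 1.05 | 15% |

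Example at c = 20%: 0.20 + 0.80 × 0.10 = 0.28; 0.20 + 0.80 × 0.15 = 0.32; 0.32 / 0.28 = 1.14.

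**No device effect, unequal history.** With p = 10% on both devices:

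| c by group | Observed risks | Ratio |
|---|---|---|
| 20% v 20% | 28.0% v 28.0% | 1.00 |
| 20% v 25% | 28.0% v 32.5% | 1.16 |
| 20% v 30% | 28.0% v 37.0% | 1.32 |

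**What the baseline record can recover.** Take the ideal case in which every carried-over condition also shows in the baseline year. At c = 20%, the 80% of patients without a baseline record (0.80 × 686 ≈ 549 per group) still show 10% v 15%, a ratio of 1.50, with power of about 71% by the same formula instead of 37%. In the 20% v 30% case, risks are equal within each history stratum (100% v 100% and 10% v 10%), so the spurious 1.32 disappears. Real recording is less complete, so the gain would be smaller.

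**The case against.** A reader might infer that every outcome-year record counts as an event and that chronic conditions are therefore scored as harms of the device. The documents do not support that. The text speaks of incidences without defining them, chronic bronchitis is nowhere mentioned, and code lists and the merging of repeat visits may properly sit in an analysis plan that is not shown. The comparison is between two active devices, so equally common prior illness dilutes the contrast and creates no false harm. Nor does item (2) say that the eight conditions are pooled, so joint pain need not obscure thrush if the items are tested separately; an any-event rule appears only in the therapeutic index.

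A second tempting inference is that the events should be restricted to new onset, as diabetes is. Diabetes is a lasting diagnosis; most of these events can recur. The closer parallel is exacerbations, where the Protocol sets no new-onset condition and only merges events close in time ("these events will be considered to be the result of the same exacerbation"). Dropping everyone with a baseline record would also discard worsening on treatment.

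Finally, baseline counts will be tabulated by device, so an imbalance would be visible, and the study is labelled exploratory.

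All of this stands and limits the point. It leaves two things unanswered. Seeing an imbalance in a table does not remove it from an unadjusted test, and the optional matching names no variables; the listed co-morbidities include no arthritis or chronic pain. And the index formula, with its uneven use of baseline, is fixed in the Protocol itself.

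**Conclusion.** The point holds in this form: the Protocol derives each adverse event in both years, states only an unadjusted comparison between non-randomised groups, and refers the benefit term of the therapeutic index, but not its harm term, to baseline. The mismatch within the index follows from the wording alone.

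The size cannot be known from the Protocol. With the assumed new-onset risks of 10% and 15%, equal carry-over of 10% to 30% lowers the risk ratio from 1.50 to between 1.24 and 1.09, and power from 80% to between 53% and 26%. On the absolute scale the loss is milder, from 5.0 points to between 4.5 and 3.5. A false difference arises only if prior prevalence differs between devices; gaps of 5 and 10 points give ratios of 1.16 and 1.32. These figures assume that carried-over conditions are always recorded again. They concern a single yes/no event, not the repeat counts.

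**What to change.** 1. Compare each adverse event between devices in a regression of the outcome-year count on device, with that event's baseline-year count as a covariate: negative binomial for counts, logistic where only presence or absence is analysed. Keep the unadjusted tests as description.
2. Define the harm term of the therapeutic index relative to baseline, as no increase in adverse events over the baseline year, so that it parallels the benefit term.
3. Optionally, add a sensitivity analysis of new-onset events only for chronic-type items such as muscle or joint pain. It should not be the main analysis, because it ignores worsening, and a one-year look-back misses older disease.

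The cost is a little extra analysis on dated events already due to be extracted for both years. No new data are needed.

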STUDY DESIGN

The study will be a retrospective database analysis, consisting of a (one year) baseline period, a (one year) outcome period and an index date, defined as the date of the first prescription for Seretide[®] combination therapy at which patients with evidence of COPDⁱⁱⁱ will be split into the following groups:

- (1) Those using pMDI (also known as Evohaler)
- (2) Those using Diskus (also known as Accuhaler)

The baseline period will be one year prior to and including the index date^{iv} and it will be used for patient characterisation, such as demographics, baseline therapy, disease severity and number of COPD exacerbations. The outcome period will be one year following the index date, and the effect of device on COPD-related severe exacerbations, adverse events and therapeutic index will be investigated.

ⁱⁱⁱ COPD diagnostic code (at any time) and recorded spirometry data supporting COPD diagnosis within 5 years window of diagnosis code. Note that individuals with asthma and bronchiectasis will not be excluded.

^{iv} except for therapy prescribed at IPD (which is included in the outcome).

[figure not shown]

Figure 1: Study design

Inclusion Criteria

In order to be included in the study, patients must fit the following criteria:

- (1) COPD diagnosis (COPD diagnostic code (at any time) and COPD confirmed by FEV/FVC ratio <0.7 ever in medical history. Note that individuals with asthma and bronchiectasis will not be excluded)
- (2) Two years of continuous practice data comprising 1 year baseline data and 1 year outcome data
- (3) ≥2 prescriptions for Seretide® pMDI OR Seretide® Diskus during 1 year outcome period, inclusive of IPD (i.e. 1 Seretide® prescription at IPD plus ≥1 prescriptions for the same device during 1 year outcome period).
- (4) Age ≥35 at time of initiating with Seretide

Exclusion Criteria

- (1) Evidence of restrictive lung disease other than bronchiectasis (diagnostic code)
- (2) ≥1 prescription for inhaled corticosteroids (ICS), including as part of a fixed dose combination, during baseline period (excluding IPD)
- (3) Evidence of pneumonia during baseline period (diagnostic code)
- (4) No maintenance oral steroids in baseline

Dataset Variables

Demographics (gender, age, weight, height, BMI, smoking status, disease severity (FEV1 percent predicted, FEV1/FVC ratio, GOLD group, mMRC score)) will be calculated at (or closest to) the IPD. Disease severity will be regarded as missing if >5 years either side of IPD.

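### The therapeutic index sets outcome-year ICS dose against outcome-year events without requiring the dose to come first, so doses changed in response to events can be read as their cause

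*Protocol*

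**What the plan says.** The therapeutic index is the third numbered outcome in the protocol's Study Outcomes section. It is defined causally, as "highest dose not causing harm (side effect) / lowest dose that causes benefit", and each term then gets a working rule. The numerator is "the median dose at which no (any) adverse events occur". The denominator is the "median dose at which patients show no increase in number of exacerbations in outcome".

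The dose comes from the Dataset Variables list: "ICS dose (in outcome period only) and date of ICS prescription". Study Design sets the event window: "The outcome period will be one year following the index date". Footnote iv counts therapy prescribed on the index date as outcome-period therapy. Inclusion criterion (3) requires "1 Seretide® prescription at IPD plus ≥1 prescriptions for the same device during 1 year outcome period", which fixes the device but not the dose.

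Dates are collected for exacerbations, for ICS prescriptions and for adverse events ("Number of potential severe COPD-related adverse events and date of event including"). The index definition uses none of them.

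**The concern.** Both terms sort patients by what happened over the outcome year and then take the median of a dose recorded in that same year. In routine care a dose may be raised after an exacerbation or lowered after a side effect. If the dose that enters the index is a year average or the last of the year, part of it is then a consequence of the event it is meant to explain.

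There are two routes. Patients with no adverse event cannot have had a dose change because of one, but some had an exacerbation and a later step-up, which lifts the numerator. Patients with no increase in exacerbations include some whose dose was lowered after a side effect, which pulls the denominator down. An inert dose could then give an index above 1 and be reported as a favourable balance of benefit and harm. If responsive dose changes were more common on one device, that would show as a device difference, which is what the study sets out to examine.

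**Working it through.** The protocol gives no index value, dose distribution, event rate or sample size, so there is no figure of its own to reproduce. The check has two parts.

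**1. Is there a time-order rule?** Dose window: outcome year only. Event window: the year after the index date. Later prescriptions: same device, dose unrestricted. Index rule: two medians, with no dose (first, mean, last, or in force at the event) named and no date comparison. So an analysis that followed the text with a mean or last dose would comply and would let a post-event dose classify that event.

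**2. What would that do when dose has no effect?** Write D for the patient's dose.

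Index = median(D among patients with no adverse event) / median(D among patients with no increase in exacerbations)

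In the simulation dose affects neither outcome, so the true index is 1. Every input is an assumption:
- 1,000,000 patients per scenario; log-normal starting dose, median 1, log-SD 0.5
- adverse events 0.3 or 0.8 per year; exacerbations 0.5 or 1.0 per year, with gamma frailty shared by the baseline and outcome years
- dose halved with probability 0, 0.1 or 0.3 at the first adverse event
- dose doubled with probability 0, 0.1 or 0.3 at the first exacerbation

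Results at 0.8 adverse events and 1.0 exacerbations per year (medians are rounded, so a quotient may differ in the last digit):

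| Halved / doubled | Dose used | No-AE median | No-increase median | Index |
|---|---|---|---|---|
| 0 / 0 | last | 1.001 | 1.001 | 1.000 |
| 0.3 / 0 | year mean | 1.000 | 0.949 | 1.054 |
| 0.3 / 0 | last | 1.000 | 0.908 | 1.101 |
| 0 / 0.3 | year mean | 1.063 | 1.036 | 1.026 |
| 0 / 0.3 | last | 1.089 | 1.053 | 1.034 |
| 0.1 / 0.1 | year mean | 1.021 | 0.994 | 1.027 |
| 0.1 / 0.1 | last | 1.029 | 0.987 | 1.042 |
| 0.3 / 0.3 | year mean | 1.062 | 0.982 | 1.082 |
| 0.3 / 0.3 | last | 1.089 | 0.956 | 1.140 |

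Over all scenarios with responsive dose changes, the index was 1.014 to 1.082 with the year-mean dose and 1.023 to 1.140 with the last dose. With no responsive changes it was 1.000. With the index-date dose it was 0.999 to 1.001 throughout.

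**Two dose levels instead of a continuous dose.** Assumptions: levels in a 1:2 ratio; 25% of lower-dose patients with an exacerbation stepped up; 30% of higher-dose patients with an adverse event stepped down; 0.8 exacerbations per year; 30% with an adverse event. The mean-dose and last-dose index was 1.00 when 20, 30, 40, 60, 70 or 80% started on the higher level. It left 1.0 only for starting shares of roughly 44 to 54%. With 10% stepped up and 10% stepped down, only about 48 to 50% was affected.

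**The case against.** The strongest reply is that the protocol never commits to a mean or last dose. The index-date prescription is part of the outcome data, the dates allow ordering, and the phrase about the dose at which events occur could mean the dose in force at the time. Which prescription supplies a patient's dose is the kind of rule a statistical analysis plan may hold, and that plan is not at hand. This stands in part: it means that post-event doses can enter the index, not that they will. It does not remove the point, because the protocol sets the formula for a numbered outcome itself, words it causally, and leaves it open to a compliant but biased choice.

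A reader might infer more than the documents support in four ways:

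- **That both terms always move in favour.** They do not. With step-ups only, the denominator rises too (1.053 in the table), because patients who exacerbated no more often than before may still have been stepped up. The index exceeds 1 there only because the numerator rises more.
- **That the index could double.** With two levels in a 1:2 ratio the last-dose index can reach 2.0, but only near an even starting split, where a median jumps from one level to the other. That is a property of medians on discrete doses and is not a typical size.
- **That dose-event odds ratios measure the harm.** The protocol plans no such analysis, so they would not describe bias in its index.
- **That the device comparison is biased.** If responsive dose changing is alike in both arms, the distortion largely cancels. No passage shows that it differs.

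Lower respiratory tract infection and bronchitis are listed adverse events and may coincide with exacerbations. If 30 to 60% of exacerbators also carry an adverse-event code (assumed), the last-dose index in one scenario falls from 1.081 to between 1.066 and 1.049. The bias shrinks but does not reverse. It disappears only when step-ups are the sole dose change and the overlap is high.

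**Conclusion.** The point holds in limited form. The index is worded causally, takes its dose from the same year as the events, and has no rule that the dose precede the event. Under a mean-dose or last-dose reading, reverse causation tends to push it above 1 when dose does nothing.

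The size rests wholly on assumed event rates, step-up and step-down probabilities and dose distribution, none of which the protocol gives. It is about 1 to 14% with a continuous dose, and nil with two levels unless the starting split is near 50%. The simulation shows mechanism and usual direction and does not predict what this study would find. A spurious device difference needs dose-change habits that differ by device. In a study labelled exploratory, this is a cheap improvement and not a fatal defect.

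**What to change.** In the therapeutic index definition, state that each patient's dose is the daily fluticasone dose of the index-date (IPD) prescription, which footnote iv already keeps in the outcome data. Add that doses prescribed after an event are not used to classify that event. The dose in force immediately before the first event, from the recorded prescription and event dates, can serve as a sensitivity analysis.

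The cost is one or two derivation sentences, plus a date comparison for the sensitivity analysis, all on fields already extracted. There are two limits. The index-date dose ignores later titration. Putting dose before event also does not remove confounding of the starting dose by severity, so the causal wording of the index would still need caution.

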Study 1: Exploratory study - identifying the benefits of pMDI versus Diskus for delivering fluticasone/salmeterol combination therapy in patients with chronic obstructive pulmonary disease (COPD)

Version Date: 7 February 2014

Protocol

**Study 1: Exploratory study -
identifying the benefits of pMDI
versus Diskus for delivering
fluticasone/salmeterol combination
therapy in patients with chronic
obstructive pulmonary disease
(COPD)**

To characterise patients with COPD initiating with fluticasone/salmeterol combination therapy via pMDI and Diskus and to identify and compare the potential benefits of using either device in the delivery of fluticasone/salmeterol combination therapy

Contents

OBJECTIVES	3
BACKGROUND	3
DATASOURCE	4
STUDY DESIGN	4
STUDY OUTCOMES	7
STATISTICAL ANALYSIS.....	8
TIMELINE, DELIVERY AND COSTINGS	9
RESEARCH TEAM	9
REFERENCES.....	9

OBJECTIVES

The aims of this exploratory study are to characterise patients with chronic obstructive pulmonary diseaseⁱ (COPD) initiating with fluticasone/salmeterol combination therapy delivered via pressurised metered dose inhaler (pMDI; also known as Evohaler) or Diskus (also known as Accuhaler); and to identify and compare the potential benefits of using either device in the delivery of fluticasone/salmeterol combination therapy.

This will be carried out by:

- (1) Characterising patients with COPD on fluticasone/salmeterol combination therapy via pMDI and Diskus.
- (2) Identifying and comparing the potential benefits of using pMDI versus Diskus in the delivery of fluticasone/salmeterol combination therapy in terms of both efficacy and adverse events, in particular:
 - a. Number of COPD exacerbations
 - b. Development of pneumonia infections
 - c. Type II diabetes diagnosis
 - d. Therapeutic indexⁱⁱ
 - e. Number of severe COPD-related events, including:
 - i. Lower respiratory tract infections
 - ii. Oral thrush

These are more clearly defined under 'Dataset Variables' below.

BACKGROUND

Inhaled corticosteroid use by patients with obstructive lung disease is associated with increased risk of pneumonia [1], increased risk of developing type-II diabetes [2] and increased risk of oral thrush [3].

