Pressurised metred dose inhaler (pMDI) and Diskus devices both deliver fluticasone/salmeterol combination therapy, but the Diskus formulation includes added lactose. A previous Research in Real Life study [4] demonstrated that asthma patients on combination therapy via pMDI have significantly greater odds of achieving asthma control and fewer exacerbations than those on dry powder inhalers such as Diskus.

This study aims to explore and identify the benefits of using either pMDI versus Diskus for delivering fluticasone/salmeterol combination therapy in patients with COPD.

This study will focus on patients with COPD initiating with Seretide[®] combination therapy, delivered via

- pMDI (also known as Evohaler)
- Diskus (also known as Accuhaler)

In addition, the number of patients in the following sub-populations will be reported:

ⁱ COPD is defined as a common, preventable and treatable disease characterised by persistent airflow limitation that is usually progressive and associated with an enhanced chronic inflammatory response in the airways and lungs to noxious particles and gases.

ⁱⁱ Therapeutic index = highest dose not causing harm (side effect) / lowest dose that causes benefit (reduced number of severe COPD-related events).

- COPD without asthma
- COPD with asthma
- COPD +/- asthma AND eosinophils $>0.4 \times 10^9/L$

DATASOURCE

This study will use the Optimum Patient Care Research Database (OPCRD), which comprises anonymous data extracted from primary care practices in order to perform reviews of their chronic respiratory services. Two types of anonymised patient data are typically collected:

- (1) Routine clinical data
 - OPC software interfaces with primary care practice management systems and extracts disease coding and prescribing information.
- (2) Questionnaires
 - Patients identified as recipients of the respiratory service under review are invited to complete validated disease assessment questionnaires to better understand their current health status (and/or possible reasons for sub-optimal status).
 - Anonymised questionnaires are assigned a unique code to aid matching routine data to questionnaire results.

The OPCRD has been approved by Trent Multi Centre Research Ethics Committee for clinical research use. The anonymous, longitudinal patient data offers a high-quality data source for use in clinical, epidemiological and pharmaceutical research. It enables research to be carried out across a broad range of respiratory areas.

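### The therapeutic index, as calculated, does not estimate the highest-harmless over lowest-beneficial dose ratio that the protocol defines

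*Protocol*

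**What the plan says.** Footnote ii of the Background and item (3) of Study Outcomes give the same definition: "Therapeutic index = highest dose not causing harm (side effect) / lowest dose that causes benefit (reduced number of severe COPD-related events").

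Item (3) then says how each part is obtained:

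- Numerator: "For the highest dose not causing harm: the median dose at which no (any) adverse events occur".
- Denominator: "median dose at which patients show no increase in number of exacerbations in outcome".

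Under Dataset Variables, the dose information to be collected is "ICS dose (in outcome period only) and date of ICS prescription". Footnote iv in Study Design counts therapy prescribed at the index date as part of the outcome period.

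The index is one of three numbered outcomes on which the effect of device will be investigated, and the only one that combines benefit with harm. The protocol states no dose levels, dose distribution, exacerbation rate, adverse event rate or expected index value.

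**The concern.** A therapeutic index is meant to say how wide the margin is between a dose that helps and a dose that harms. That requires two thresholds read from dose-response relations. The protocol instead takes the middle dose among patients selected by how their outcome year went. Such a median mainly reflects what was prescribed.

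Two devices could differ greatly in exacerbations or side effects and still give the same index. They could also give different indices only because their prescribing mixes differ. Either result would be reported as a statement about benefit-harm balance.

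**Working it through.** **1. Definition against calculation**

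| Element | Definition | Calculation |
|---|---|---|
| Numerator dose | highest | median |
| Denominator dose | lowest | median |
| Benefit | fewer events | no rise in events |
| Event counted | severe COPD-related events | exacerbations |
| Harm | no side effect | "the median dose at which no (any) adverse events occur" |

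The last row can mean patients with no adverse event, or patients with any. On the fourth row, the Objectives list lower respiratory tract infection and oral thrush as severe COPD-related events, and Study Outcomes (2) lists the same two as adverse events. The definition therefore leaves their side of the ratio unclear.

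**2. What "no increase" admits**

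Assume that nothing changes between the years, with 0.9 exacerbations per year and gamma-distributed patient rates of shape 1. Write m = 0.9.

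- P(same count in both years) = 1/√(1 + 4m) = 1/√4.6 = 0.466
- P(reduction) = (1 − 0.466)/2 = 0.267
- P(no increase) = 0.466 + 0.267 = 0.733
- P(zero in both years) = 1/(1 + 2m) = 1/2.8 = 0.357, which is 0.357/0.733 = 49% of the no-increase group

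With no effect at all, 73% would count as showing benefit, against 27% with a reduction. About half of those counted had no exacerbation to prevent in either year.

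**3. Risk unrelated to dose**

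Let S be membership of either subgroup within one device arm. If S is independent of dose, then median(dose | S) = median(dose). Numerator and denominator are equal and the index is 1. The level of risk does not enter, so a device effect that is the same at every dose is invisible. This needs no assumed rate. Simulation of the index as worded (400,000 patients per scenario, continuous dose) gave 1.00 in all 12 such scenarios, with assumed outcome exacerbation rates of 0.3 to 1.5 per year and adverse event risks of 0.1 to 0.5.

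**4. Risk related to dose**

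If harm rises with dose, event-free patients are on lower doses and the numerator falls. If benefit rises with dose, patients without an increase are on higher doses and the denominator rises. Both lower the index, so it cannot tell them apart. Simulated with continuous lognormal dose (assumed median 500, log SD 0.6):

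| Assumed gradient per dose doubling | Index |
|---|---|
| Adverse event OR 1.3, exacerbation rate ratio 0.85 | 0.91 to 0.97 |
| OR up to 4, rate ratio down to 0.5 | as low as 0.61 |
| Full range, "no adverse event" reading | 0.61 to 1.00 |
| Full range, "any adverse event" reading | 0.89 to 1.69 |

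**5. A few discrete strengths**

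Assume doses 200, 500 and 1000, adverse event risk 0.3 at dose 500, OR 1.5 per doubling, and no dose effect on exacerbations. The event-free proportion is 1/(1 + (0.3/0.7) × 1.5^log2(dose/500)), which gives 0.800, 0.700 and 0.609.

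*Mix 10% / 38% / 52%*

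- Event-free weights: 0.080, 0.266 and 0.317, total 0.662.
- Share on the top dose: 0.317/0.662 = 47.8%, below half, so the numerator is 500.
- Among no-increase patients the top-dose share stays at 52%, so the denominator is 1000.
- Index = 500/1000 = 0.5.
- On the "any adverse event" reading, the top-dose share is 60.3%, the numerator is 1000 and the index is 1.0.

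*Mix 30% / 50% / 20%, same risks*

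- Event-free shares: 33.7%, 49.2% and 17.1%, so the numerator is 500.
- Denominator: 500.
- Index = 1.0.

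The effects are identical and only the prescribing mix differs, yet the index halves. In another simulated case, an exact 50/50 split at the boundary with no effect at all gave 2.

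**6. Would rewording the denominator alone help?**

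With continuous dose, requiring a true reduction but keeping medians gave 0.57 to 1.00, against 0.61 to 1.00 as worded. It does not help, because the fault lies in taking medians of outcome-selected patients.

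**The case against.** The study is titled exploratory, and the index is listed third among outcomes introduced as being among others. Exacerbations and adverse events are each compared by device directly, so benefit and harm stay visible without it. This stands, and it lowers the severity.

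A reader might infer several stronger charges that the document does not support:

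- *The index is about 1 whatever the device does.* It is not. Strong dose gradients move it well below 1, and discrete doses can make it jump. The invariance holds only when risk does not vary with dose.
- *The medians agree because the two groups are largely the same, event-free patients.* No event rates are given, and the adverse event list is broad (colds, bronchitis, muscle or joint pain). In simulation the overlap (intersection over union) ranged from 0.25 to 0.83. Equal medians come from membership being unrelated to dose.
- *Dose is distorted by the very events it should explain.* This is possible but not fixed by the text. The outcome period includes the index prescription, and the protocol does not say which dose enters the index. Recording dose only in that period also follows from excluding baseline users of inhaled corticosteroids.
- *The index has no measure of uncertainty.* An interval may be specified in an analysis plan that is not shown.

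None of this touches the mismatch between definition and calculation, which the protocol itself fixes.

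**Conclusion.** The point holds in this limited form. The mismatch and the ambiguous numerator can be read directly from the text. The value of 1 under dose-independent risk, and the fall when benefit rises with dose, follow from the formula. All other sizes depend on assumed rates, gradients and doses and should be read as illustrations. The index as calculated cannot be interpreted as a therapeutic margin or used to rank the devices on benefit against harm. It should be fixed before analysis, but it does not undermine the study's other comparisons.

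**What to change.** Drop the median ratio as the benefit-harm comparison. Take the dose on the index prescription as exposure and fit adjusted dose-by-device models for two outcomes:

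1. the exacerbation count in the outcome year, with the baseline count as covariate;
2. occurrence of any of the listed adverse events.

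Report the between-device difference in each, by dose stratum, with 95% confidence intervals.

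If the ratio is kept, label it descriptive, remove the highest-dose and lowest-dose interpretation, and state whether the numerator uses patients with no adverse event or with any.

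The cost is protocol or analysis-plan wording and some programming. ICS dose and prescription dates are already on the variable list, so no new data are needed. The single-number summary is lost, and a dose stratum is informative only where both devices were prescribed in it.
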